0. REVISION HISTORY

1. STUDY DESIGN

1.1. Description of Study Design

This clinical study is a multicenter, open-label extension study. Subjects who completed the entire double-blind, placebo-controlled, parent trial (EN3835-201) and sign an informed consent form will be eligible to participate in this study.

After the Sponsor has broken the EN3835-201 study drug blind, subjects enrolled in the open-label study will have the following options:

- To have no EN3835 treatments in study EN3835-202
- If received EN3835 in study EN3835-201, may elect to have a qualifying quadrant other than the one treated with EN3835 in study EN3835-201 (termed *re-dosing*)
- If received EN3835 in study EN3835-201 and the cellulite severity scores of the treated quadrant have returned to or are higher than EN3835-201 baseline scores, may elect to have the previously treated quadrant retreated with EN3835 (termed *re-treatment*)
- If received placebo in study EN3835-201, may elect to have a qualifying quadrant treated with EN3835; also may elect to have a second qualifying quadrant treated with EN3835 after completing the treatment course

Following completion of safety and cellulite assessments at Day 71 of the double-blind study (EN3835-201), subjects will be asked if they wish to continue in the open-label extension to the double-blind study (Screening A). Subjects enrolled in study EN3835-202 who elect to receive EN3835 treatment (either re-treatment, re-dosing, or a first treatment) must meet specific inclusion and exclusion criteria for eligibility during re-screening (Screening B) prior to EN3835 dosing.

Previously placebo-treated subjects will have the option to receive a second course of EN3835 in the same or different qualifying quadrant after at least 28 days following the end of the first treatment course (eg, the Screening B visit of second quadrant could be performed on Day 71 after treating the first quadrant). The selected quadrant can be re-treatment or re-dosing.

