At each treatment course, subjects will receive 3 treatment sessions (Day 1, Day 22, and Day 43) unless the chosen quadrant has no further treatable edematous fibrosclerotic panniculopathy (EFP) dimples and the Investigator rates the quadrant a score of 0 on the Clinician Reported Photounumeric Cellulite Severity Scale (CR-PCSS). The same dimples within a quadrant or different dimples within a quadrant may be treated at each session but injections must all be within the selected quadrant for all 3 sessions. Each treatment session will be separated by approximately 21 days. Day 71 visit (end of treatment/early termination [EOT/ET]) will be performed for each subject. After Day 71, the subjects will be observed every 3 months from their first exposure to EN3835 up to a maximum of 1 year in each treated quadrant (including

both open-label and double-blind treated quadrants, if different quadrants were treated across both studies). Durability beyond Day 360 will be assessed in subjects who received active treatment in EN3835-201 and showed a composite improvement of at least 1 level on both the CR-PCSS and the Patient Reported Photonic Cellulite Severity Scale (PR-PCSS). In these subjects, the original quadrant treated in EN3835-201 will be assessed until the end of the current study, in addition to any treated quadrants occurring in the current study. Assessments of durability beyond Day 360 may also include subjects who opted not to receive additional treatments in EN3835-202.

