• Hexsel Cellulite Severity Scale (CSS)	X ^{h,i}				X ^h	
• Investigator Global Aesthetic Improvement (I-GAIS)					X ^h	
Confirm Eligibility	X	X ^e				
Select Quadrant	X ^j					
Study drug administration		X	X	X		
Injection site reactions/local tolerability in selected quadrant		X	X	X	X	
Adverse events			Monitored Throughout Study			

^a After the study drug blind is broken in study EN3835-201, eligible subjects may elect to receive EN3835 treatments.

^b Upon completion of treatment, subject will be followed at 3-month intervals as in [Table 2](#); if study terminates early, subject will be followed through Visit 4 (Day 71). If subject received placebo in the double-blind study (EN3835-201), she may be eligible for a total of 2 courses of treatment (a total of 6 treatment sessions) in this study.

^c All 4 quadrants are photographed at screening; at other visits, the selected quadrant only is photographed.

^d Before and after marking the dimples.

^e Before injection.

^f Up to 4 hours before injection; approximately 15 and 30 minutes after injection. Vital signs must be stable before the subject is discharged.

^g Assessment made via photograph (if treatment session, use photograph taken before marking dimples).

^h All 4 quadrants are assessed at the Screening B visit; at other visits, the selected quadrant only is assessed.

ⁱ Initial Hexsel CSS at screening must be ≤ 13 on selected quadrant.

^j To qualify for treatment, the selected quadrant must have a score of 3 or 4 (moderate or severe) in both the CR-PCSS and PR-PCSS, and a Hexsel CSS score ≤ 13 ; to qualify a quadrant that had been previously treated with EN3835 in study EN3835-201, the quadrant must have CR-PCSS and PR-PCSS scores equal to or greater than study EN3835-201 baseline scores and a Hexsel CSS score ≤ 13 .

^k Medical history and prior medications will be based on EN3835-201 eCRF; only updates and concomitant medications need to be captured at Screening B visit.

^l Do not conduct if Screening B visit date is within 12 months of obtaining an ECG during the double-blind study (EN3835-201).

^m Do not conduct on subjects eligible and opting-in for a second course of treatment in the current study (EN3835-202) if Screening B visit or Day 1 visit for second treatment course is the same day as Day 71 of the first treatment course in this study or previous study EN3835-201.

ECG=Electrocardiogram; eCRF=Electronic case report form; EFP=Edematous fibrosclerotic panniculopathy; Tx=Treatment

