2. ANALYSIS POPULATIONS AND PHASES

The following populations will be considered in the statistical analysis of the study:

- Observation Population: The Observation population includes all subjects rolled over from study EN3835-201. The cellulite assessment evaluations and safety analyses on data collected during observation phase will be performed using this population.
- Safety Population: The Safety population will include all subjects who receive at least 1 dose of EN3835 in the current study. All safety analyses for the treatment phase will be performed using this population. For by region summaries, safety population is considered within each treatment course.
- Effectiveness Population: The Effectiveness population includes all safety subjects who have a baseline and at least 1 post-baseline assessment on both the CR-PCSS and PR-PCSS on the quadrant selected for treatment in the current study. All analysis of effectiveness for the treatment phase will be based on this population. For by region summaries, effectiveness population is considered within each treatment course.
- Durability Population: This population is defined as all active responders who have both CR-PCSS and PR-PCSS at 180 days or above. The active responders are subjects treated with EN3835 with improvements of at least 1 level on each

scale (CR-PCSS and PR-PCSS) at Day 71 visit compared to the baseline. Analysis of durability of treatment effect will be performed using this population.

- Durability Population for Double-blind Treated Subjects: This population is defined as all subjects in the durability population who showed an improvement of at least 1 level on each scale (CR-PCSS and PR-PCSS) at Day 71 visit compared to the baseline for the quadrant treated with EN3835 in double-blind study EN3835-201.
- Durability Population for Open-label Treated Subjects: This population is defined as all subjects in the durability population who showed an improvement of at least 1 level on each scale (CR-PCSS and PR-PCSS) at Day 71 visit compared to the baseline for the quadrant treated with EN3835 in the open-label study EN3835-202 study, who did not have the same quadrant treated with EN3835 in double-blind study EN3835-201. For by region summaries, this population is considered within each treatment course.

The following 2 phases will be summarized in the statistical analysis of the study:

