- Observation phase: Observation phase is defined as the time period from Screening A to the first treatment date of the same quadrant in study EN3835-202 or the end of study EN3835-202 if there is no treatment received for the same quadrant in study EN3835-202. Observation phase is defined within each treated quadrant, unless the summary is for subject level only and cannot be differentiated by the treated quadrant, ie, disposition, adverse event (AE). For subject level summaries, observation phase is defined as the time period from Screening A to the first treatment date in study EN3835-202 or the end of study EN3835-202 if there is no treatment received in study EN3835-202.
- Treatment phase: Treatment phase is defined as the time period from the first treatment date of certain quadrant in study EN3835-202 to the end of study EN3835-202. Treatment phase is defined within each treated quadrant, unless the summary is for subject level only and cannot be differentiated by the treated quadrant, ie, disposition, AE. For subject level summaries, treatment phase is defined as the time period from the first treatment date to the end of study EN3835-202.

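### The SAP does not say where course-1 follow-up ends when a former-placebo woman has a second EN3835 course in the same quadrant, so ratings after Day 71 can mix two courses

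*Combined protocol and SAP*

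**What the plan says.** SAP section 2 defines two phases at quadrant level. The observation phase runs only "to the first treatment date of the same quadrant in study EN3835-202", or to study end if that quadrant is not injected. The treatment phase runs "from the first treatment date of certain quadrant in study EN3835-202 to the end of study", with no further cut.

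SAP 1.1 gives former-placebo women the "option to receive a second course of EN3835 in the same or different qualifying quadrant after at least 28 days" from the end of the first. It follows women "every 3 months from their first exposure to EN3835 up to a maximum of 1 year in each treated quadrant".

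Two provisions deal with repeat exposure of one quadrant, and both look back only to the parent study:
- The open-label durability population is limited to Day 71 responders "who did not have the same quadrant treated with EN3835 in double-blind study EN3835-201".
- Footnote j of SAP Table 3 requires scores at or above the parent-study baseline only "to qualify a quadrant that had been previously treated with EN3835 in study EN3835-201".

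Courses are separated in places. For by-region summaries, the safety, effectiveness and open-label durability populations are taken one course at a time (section 2). Section 6.2.2 mentions by-course summaries as an example. Exposure, administration, TEAEs and immunogenicity are split by course (7.2, 7.3, 7.4, 7.7). Sections 6.2.1 (composite response) and 6.3 (durability) contain no by-course rule.

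Protocol 12.1.4 placed a same-quadrant second course in a re-treatment arm. SAP section 9 replaces the protocol's cohort-based analysis with phases and populations.

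**The concern.** The observation phase stops when the same quadrant is injected, because later ratings no longer describe the earlier exposure. The same logic applies when course 2 follows course 1 in one quadrant, but nothing equivalent is written there.

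Read literally, a Day 180 rating on the first-exposure clock is course-1 follow-up even if course 2 has been given in between. One-year figures would then describe up to six sessions while being read as the result of three. A woman not responding at Day 71 could appear as a late course-1 responder in 6.2. A Day 71 responder who was losing response, or had responded only partly, could be counted as maintained in 6.3. Two programmers following the same SAP could produce different one-year percentages.

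**Working it through.** **1. Earliest start of course 2.** The last course-1 session is Day 43 and the minimum gap is 28 days: 43 + 28 = 71. This reproduces protocol 10.1, which allows the next treatment from Day 71. SAP 1.1 gives Day 71 as an example for the second Screening B. Footnote m of SAP Table 3 allows for either Screening B or Day 1 of course 2 on that day.

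**2. Visits after course 2.** For a course-2 start on course-1 day s, a visit on course-1 day v falls on course-2 day v − s + 1. The start days below are illustrative, apart from the earliest, Day 71.

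| Course-2 start | Day 90 | Day 180 | Day 270 | Day 360 |
|---|---|---|---|---|
| Day 71 | 20 | 110 | 200 | 290 |
| Day 100 | before | 81 | 171 | 261 |
| Day 200 | before | before | 71 | 161 |

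Between two and four of the four later visits are exposed. The Day 71 result is not, because its ratings precede any same-day injection.

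**3. Who can requalify.** Treatment requires 3 or 4 on both scales. A durability responder has improved at least 1 level on both at Day 71. By baseline (CR-PCSS/PR-PCSS):

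| Baseline | Responder still eligible at Day 71? | Lowest qualifying score, 3/3, against baseline |
|---|---|---|
| 3/3 | No; at best 2 on both | Back to baseline on both: meets the 6.3 failure definition |
| 3/4 or 4/3 | No; one scale is at most 2 | Back to baseline on one scale, 1 level better on the other |
| 4/4 | Yes, at 3/3 only | 1 level better on both: still a responder |

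No 2-level composite responder is eligible at Day 71, since the highest score she can have is 4 − 2 = 2.

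**4. Backward imputation.** SAP 8.1 gives the example of filling missed Days 90 and 180 from Day 270. If course 2 began on Day 200, Day 270 is course-2 Day 71. That rating would then stand as course-1 Day 90 and Day 180, both before course 2.

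**5. Entry to the durability set.** Section 2 also requires both ratings at 180 days or later. If course 2 starts before then, that qualifying rating may itself follow it.

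**6. Size.** The affected women are a subset of former-placebo women, who are about half of those enrolled (333/2 ≈ 166 from protocol 17.1, given 1:1 randomisation in the parent study). How many would take a same-quadrant second course is not stated. As an assumption only, let a share f of a late-visit denominator be retreated in the same quadrant, let a share r of those be rated responders afterwards, and let none have been responders otherwise. The rate then rises by 100 × f × r points:
- f = 0.05, r = 0.30: 1.5 points
- f = 0.30, r = 0.60: 18 points

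**7. Why a date cut alone is not enough.** Assume 20% of responders are retreated, with single-course maintenance of 20% in them and 57.5% in the rest. The single-course figure is 0.20 × 20 + 0.80 × 57.5 = 50%. Dropping retreated women reports 57.5%. Keeping them and counting retreatment as loss reports 0.80 × 57.5 = 46%.

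**The case against.** The strongest reply is that the SAP already works by course. The populations are split by course for by-region summaries, 6.2.2 allows by-course tables, and the treatment phase may be meant only to separate treatment data from observation data. A reader might infer that the SAP reports course-2 effect as course-1 response. It does not say so, and the within-course wording points the other way. What remains is that this wording settles who is counted, not which visits count. A woman can belong to both course populations. Overall summaries, 6.2.1 and 6.3 are not covered.

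A reader might also infer that Day 71 non-responders who improve after course 2 raise durability. They cannot enter the course-1 durability set, which holds only Day 71 responders. Their effect is confined to late response rates in 6.2.

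Relapse is partly handled: a responder with baseline 3/3 must already meet the failure definition to requalify. That helps only if the requalifying rating is counted. Section 6.3 tabulates failure by study day and does not name Screening B. It does not help for baselines of 4/4, 3/4 or 4/3.

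The baseline is less open than SAP 3.2 alone suggests. Footnote m does not waive the severity ratings for a second course, and protocol 12.1.4 makes Screening B the baseline. The data for a course-specific baseline will exist, and only the statement is missing.

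**Conclusion.** The gap is real but limited. The SAP has no rule that ends or censors course-1 follow-up at a same-quadrant second course within EN3835-202. Ratings after course 2 can therefore enter course-1 response at Days 90 to 360 and open-label durability, directly or through backward imputation. Where this happens, it is expected to favour the drug.

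Course-1 Day 71 results are not affected. Nor is the primary objective, which is safety. A reader might infer that the headline durability evidence is compromised. Both durability objectives in SAP 1.3.2 concern women given active drug in EN3835-201. Those women have their own durability population, and the observation phase for that quadrant ends if it is retreated.

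The size cannot be estimated: the documents give neither the frequency of same-quadrant second courses nor response after one or two courses. The 1.5 to 18 points above rest wholly on assumed inputs and should not be quoted as an expected bias. The affected summaries are secondary, descriptive and confined to a former-placebo subset. This should be settled before database lock, but it does not undermine the study's main purpose.

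**What to change.** - **SAP 2:** end each course's effectiveness and durability window at Day 1, before injection, of the next EN3835 course in the same quadrant. Apply this to by-region and overall summaries.
- **SAP 6.3:** keep retreated responders in the denominator, including those whose only ratings at 180 days or later follow course 2. Count same-quadrant retreatment as loss of course-1 response from that date. Add a sensitivity summary that censors at retreatment.
- **SAP 8.1:** do not impute CR-PCSS or PR-PCSS backward across the start of course 2.
- **SAP 3.2:** state that course 2 is measured from its own pre-course baseline, and report it separately.

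The cost is SAP wording and a date cut in programming, with no new data. There will be fewer course-1 ratings after Day 71, and the one-year open-label durability figure will be somewhat less favourable. Counting retreatment as loss answers a specific question, namely response maintained without a further course in that quadrant, and the table should be labelled that way.

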3. STATISTICAL METHODS AND CONSIDERATIONS

3.1. Descriptive Statistics

All analysis results will be presented in summary table using appropriate descriptive statistics, unless otherwise stated. The statistics include the number (count) and percentage for all categorical variables. The denominator will be based on the number of subjects in each column group in the summary table, unless otherwise stated. All continuous variables will be summarized with observed count, mean, standard deviation, median, minimum, and maximum value.

3.2. Baseline Considerations

The baselines for all cellulite assessments, including CR-PCSS, PR-PCSS, and Hexsel CSS will be the observed values at visit Day 1 before subjects receive EN3835 treatment. If the values at Day 1 are missing, the values at Screening will be used for those assessments. For observation phase before EN3835 treatment in current study, the baselines will be the values at Day 1 for study EN3835-201. The reference values will be the observed scores at Day 71 in study EN3835-201 for those assessments. For the potentially clinically importance (PCI) calculation for vital sign values, the baseline refers to the latest vital sign assessment values before the first treatment in study EN3835-202.

All baselines for safety measures, ie, vital signs, clinical laboratory parameters, will use the latest values before subjects receive the first treatment in study EN3835-202.

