7.5. Vital Signs

Descriptive statistics for vital signs (body weight, body mass index [BMI], systolic and diastolic blood pressure, pulse rate, respiratory rate, and temperature) and their changes from baseline at each visit and at the end of treatment visit will be presented.

Vital sign values are potentially clinically important (PCI) if they meet both the observed value criteria and the change from baseline criteria. The criteria for PCI vital sign values are detailed

in [Appendix A](#). The baseline in PCI rules refers to the latest vital sign assessment values before the first treatment in study EN3835-202.

A listing of all subjects with PCI vital signs will also be provided.

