APPENDIX A. PCI CRITERIA

Laboratory Values

Test	Low	High
Platelets ($10^9/L$)	≤ 100	≥ 650
Hemoglobin (g/L)	≤ 100	≥ 190
Hematocrit	≤ 0.3	≥ 0.6
ALT	---	$\geq 3 \times ULN$
AST	---	$\geq 3 \times ULN$
Creatinine ($\mu\text{mol}/L$)	---	≥ 300
BUN (mmol/L)	---	≥ 12

Vital Signs

Test	Low	High
Systolic Blood Pressure	≤ 90 mmHg and decrease ≥ 20 mmHg from baseline	≥ 180 mmHg and increase ≥ 20 mmHg from baseline
Diastolic Blood Pressure	≤ 50 mmHg and decrease ≥ 15 mmHg from baseline	≥ 105 mmHg and increase ≥ 15 mmHg from baseline
Pulse Rate	≤ 50 bpm and decrease ≥ 15 bpm from baseline	≥ 120 bpm and increase ≥ 15 bpm from baseline
Respiratory Rate	≤ 8 brpm and decrease ≥ 7 brpm from baseline	≥ 25 brpm and increase ≥ 7 brpm from baseline
Temperature	---	$\geq 38.3^\circ\text{C}$ and increase $\geq 1.1^\circ\text{C}$ from baseline

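### The 15- and 30-minute post-injection vital signs are compared only with the value before the first 202 treatment, so from session 2 onward acute changes can be misclassified in the PCI listing and change summaries

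*Combined protocol and SAP*

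**What the plan says.** SAP 3.2 defines the baseline for PCI vital signs, and then for all safety measures, as values that "will use the latest values before subjects receive the first treatment in study EN3835-202". SAP 7.5 says it again: "The baseline in PCI rules refers to the latest vital sign assessment values before the first treatment in study EN3835-202". Neither section resets the baseline by session or by treatment course.

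A vital sign is PCI "if they meet both the observed value criteria and the change from baseline criteria". For low values, SAP Appendix A requires:

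- systolic pressure "≤ 90 mmHg and decrease ≥ 20 mmHg from baseline"
- diastolic pressure "≤ 50 mmHg and decrease ≥ 15 mmHg from baseline"
- pulse "≤ 50 bpm and decrease ≥ 15 bpm from baseline"

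SAP Table 3, note f, gives the timing at each treatment session: "Up to 4 hours before injection; approximately 15 and 30 minutes after injection". Protocol Table 11 has the same schedule, with temperature taken before treatment and at 30 minutes only.

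SAP 7.5 plans descriptive statistics for values and changes at each visit, and a listing of subjects with PCI vital signs. It does not mention a comparison of post-injection readings with the pre-injection reading of the same day. Protocol 17.6 refers vital-sign change to the Day 1 pre-injection reading but attaches it to each injection day, which can be read either way. SAP section 9, on changes to planned analyses, is silent on this.

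**The concern.** Readings at 15 and 30 minutes after an injection are informative mainly about what the injection did. The protocol calls EN3835 a foreign protein and requires 30 minutes of direct observation for immediate immunological events (section 12.1.4.2). The natural reference for these readings is the value taken earlier the same day. It is collected at every session, but the SAP does not use it as a reference after the first.

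Because the PCI rule needs both an absolute limit and a change limit, the choice of baseline decides who appears in the listing. With an old baseline, a woman whose pressure has drifted up since Day 1 can have a large fall after injection and stay off the list. One whose pressure had drifted down before the needle can be listed although the injection changed nothing.

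The SAP works by course elsewhere: treatment-emergent events (7.4), exposure (7.2) and immunogenicity (7.7) are all defined or summarised by treatment course. The vital-sign baseline stays tied to the first treatment in 202.

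**Working it through.** The plan states no figure for this, so there is none to reproduce. The check applies the Appendix A thresholds to example readings and then shows how far any rate depends on assumptions.

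**Age of the fixed baseline (nominal days).** Session 2: 22 − 1 = 21. Session 3: 43 − 1 = 42. Second course, Day 1: at least 71 − 1 = 70. Second course, Day 43: at least 70 + 42 = 112, or 16 weeks. At session 1 of course 1 the baseline is normally that day's pre-injection reading, so nothing goes wrong there.

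**Worked readings** (fixed baseline / same-day pre-injection / post-injection). All post values meet the absolute limit.

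| Measure | Readings | Change from fixed baseline | SAP flag | Same-day change | Same-day flag |
|---|---|---|---|---|---|
| Systolic | 100 / 108 / 86 | 14 | no | 22 | yes |
| Systolic | 110 / 88 / 88 | 22 | yes | 0 | no |
| Diastolic | 64 / 76 / 50 | 14 | no | 26 | yes |
| Diastolic | 80 / 54 / 50 | 30 | yes | 4 | no |
| Pulse | 63 / 75 / 50 | 13 | no | 25 | yes |

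These use only the thresholds in Appendix A.

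**Who can be missed.** A systolic reading of 90 or less automatically satisfies the 20 mmHg limb if the fixed baseline is at least 90 + 20 = 110. A miss therefore needs a fixed baseline below 110. The corresponding limits are 50 + 15 = 65 for diastolic pressure and for low pulse. The high-pulse rule (at least 120 bpm and up by at least 15) is little affected: a reading of 120 fails the change limb only if the fixed baseline exceeds 120 − 15 = 105.

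**Rates under assumed variability, systolic rule, 2 million draws per scenario.** No blood-pressure distribution is in the documents, so every input here is an assumption.

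*Model A.* Usual pressure μ. Each day adds a random effect (SD 7 or 10), shared by that day's pre and post readings. Each reading has error SD 4.

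- True fall of 25 to 30 mmHg, μ 105 to 115: the fixed baseline misses 8% to 26% of readings that meet the rule against the same-day value.
- Same falls, μ 120: 4% to 8%. At μ 125: 1% to 4%.
- Fall of 40 mmHg, μ 105 to 115: 3% to 9%.
- No injection effect, μ 105 to 115: 0.1% to 4% of readings are flagged, over 99% of them without a same-day fall of 20 mmHg. That share is almost automatic: the same-day difference has SD √2 × 4 = 5.7, so 20 mmHg is about 3.5 SD.

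*Model B.* Mean 110 or 118, between-subject SD 12, visit-to-visit SD 5, 8 or 12, post-injection noise SD 5.

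- Mean shift of −20 mmHg: 19% to 27% of same-day events are missed, and 22% to 37% of fixed-baseline flags are not same-day falls of 20 mmHg.
- No shift: 0.17% to 4.98% flagged with the fixed baseline, against about 0.001% to 0.002% with the same-day reference.

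**The case against.** The strongest reply is that little turns on this flag. For vital signs SAP 7.5 plans a listing and descriptive summaries; counts and percentages of PCI values are promised only for laboratory tests (7.6). No test or stopping rule depends on it. Acute reactions also have their own route: 30 minutes of direct observation, stable vital signs before discharge, and recording of any clinically significant vital sign as an adverse event (protocol 14.8), tabulated by course under SAP 7.4. This stands. A reader might infer that acute reactions would be lost from the study; the documents do not support that.

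A second reply is that the fixed baseline is a legitimate, prespecified choice, and on one reading of protocol 17.6 it follows the protocol. This also stands in part. A woman at 88 mmHg with a pre-exposure value of 110 is correctly flagged under the SAP's own definition. It would be wrong to call that flag false; it simply says nothing about the injection just given. This is why a second reference should be added and the first kept.

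Third, a reader might infer that the problem falls on the re-exposed women. Women given active drug in 201 are re-exposed at session 1 of 202, where the baseline is normally same-day, and they may have only one course in 202. Second courses are for former placebo subjects. The documents also do not say that an acute reaction is likelier at later sessions.

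Finally, the pre-injection reading may be up to 4 hours before the injection, so a same-day fall is not necessarily a fall within 15 minutes.

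None of this answers the remaining point: the planned change summaries and PCI listing contain no measure of same-session change, although the data for one are collected.

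**Conclusion.** The point holds in a limited form. From session 2 of a first course onward, the SAP's only reference for the 15- and 30-minute readings is nominally at least 21 days old, and at least 112 days old by the last session of a second course. Two of three sessions in a first course and all three in a second are affected. That acute changes can be misclassified follows from Appendix A alone and needs no assumption.

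The frequency does rest on assumptions. The miss rate for systolic pressure ranged from about 1% to 27% over the inputs tried and shrinks as usual pressure rises, because a fixed baseline of 110 mmHg or more cannot produce a miss. No single figure should be quoted as the error rate of this trial.

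The consequence is confined to the PCI listing and the change summaries. Adverse-event capture and subject management are unaffected. It is a modest defect that is cheap to correct.

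**What to change.** In SAP 3.2 and 7.5:

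- Add, for the 15- and 30-minute readings (30-minute only for temperature), change and PCI status against that same day's pre-injection value, presented by session and treatment course.
- Keep the value before the first 202 treatment as the baseline for between-visit change, and label the two baselines separately in every output.
- State that same-session change is not calculated where that day's pre-injection reading is missing.

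Reconcile this with protocol 17.6, stating whether change on each injection day is from Day 1 or from that day's own pre-injection reading, and record the decision in SAP section 9 if it departs from the protocol.

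The cost is SAP wording and one derived variable. No new data are needed and no clinical rule changes. The downside is two labelled baselines in the vital-sign outputs.
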